2.2 Secondary Objectives

Analytical sub-aims of the protocol are to: 1) Describe characteristics of women who under-attend for cervical cancer screening in a safety net health system; 2) Explore patterns of detection and treatment of cervical pre-cancers across study arms; 3) Compare characteristics of screening participants across study arms.

We will also conduct a nested study within the randomized controlled trial to assess acceptability of and experiences with self-sample HPV testing among underscreened women in our safety net health system. The nested study has two components: a telephone survey and in-depth

qualitative interviews. In the remainder of the protocol these will be referred to as "Telephone Survey" and "Qualitative Interviews."

Because of the COVID-19 pandemic, we have revised some elements of the trial, as reflected throughout the protocol. One of these revisions includes expansion of analytic sub-aim 1 (above) to include monitoring of ambulatory, and more specifically, primary care utilization in addition to cervical cancer screening. The COVID-19 era sub-aims are: 1) To compare changes in cervical cancer screening and primary care utilization (overall and by face-to-face vs. telehealth modalities) among socioeconomic, racial/ethnic, and nativity subgroups in the 12-months following the COVID-19 emergency declaration; and 2) To compare the role of individual and neighborhood-level factors on cervical cancer screening and primary care utilization (overall and modality-specific) before and after the COVID-19 emergency declaration. In the remainder to the protocol, we will refer to COVID-19 era analytic sub-aims.

2.3 Study Type

We expect higher participation in cervical screening among those participants who receive the self-collection kit with additional patient navigation.

3 STUDY METHODS

3.1 Study Methods

Eligible women will be identified monthly through a query of the EMR database. Data will be extracted and transferred to OnCore (Forte Research Systems, Madison, WI) for randomization, storage, and data management. A computer-generated permuted block randomization scheme will be used to randomly assign individuals to the three trial arms with a 1:1:1 ratio using participants' medical record number. Randomized women will receive a study-specific identification number. Randomized women will be contacted by telephone. Those who are not reached will be contacted on 3 different days at 3 different times before being classified as unreachable. Unreachable participants will be replaced by randomly-selecting additional eligible women until the target sample size is met. Women who hang up the telephone before the scripted message is delivered will receive a second call within 10-30 minutes. Those who do not hear the full message on the second attempt will be categorized as refusers.

The 3 arms of the RCT are: Arm 1: Telephone recall (control). Participants will receive a scripted telephone recall from a trained patient navigator (PN) on behalf of Harris Health. Arm 2: Telephone recall with mailed HPV self-sampling kit (intervention). Participants in this arm will receive a scripted telephone recall from a PN on behalf of Harris Health and receive a mailed HPV self-sampling kit with a pre-paid return envelope.

Arm 3: Telephone recall with mailed HPV self-sampling kit and patient navigation (intervention plus). Participants in this arm will receive the same scripted telephone recall and mailed self-sampling kit as in Arm 2. Within 3-5 days of the kit's mail-out, participants will receive a telephone call from the PN.

Procedures for the three arms of the RCT are as follows:

Arm 1: Telephone recall (control). Participants will receive a scripted telephone recall from a trained patient navigator (PN) on behalf of Harris Health. PNs will let the patient know of the telehealth options available to Harris Health patients during the COVID-19 pandemic. Patients will be given the contact information for the call center that can walk them through the steps of accessing telehealth. PNs will also inform participants that their records indicate that they are overdue for a Pap test and that primary care, including well woman exams and Pap testing is still important during the pandemic.

Arm 2: Telephone recall with mailed HPV self-sampling kit (intervention). Participants in this arm will receive a scripted telephone recall from a PN on behalf of Harris Health and receive a mailed HPV self-sampling kit with a pre-paid return envelope. PNs will state that they are calling on behalf of Harris Health, inform participants that their records indicate that they are overdue for a Pap test, instruct them to call the scheduling department to make an appointment, and provide the scheduling department's telephone number. PNs will also state that, "as an alternative to Pap test screening, you will receive a kit in the mail that allows you to collect your own sample for cervical cancer screening and send it back to the lab for testing." PNs will confirm the patient's address and within three business days, will mail participants the self-sampling kit via the US postal service. Completed kits will be returned to Harris Health lab for HR-HPV testing (described below). Arm 2 will also receive information on telehealth options available for Harris Health patients and will be given the phone number for help accessing telehealth.

Arm 3: Telephone recall with mailed HPV self-sampling kit and patient navigation (intervention plus). Participants in this arm will receive the same scripted telephone recall and mailed self-sampling kit as in Arm 2. Within 3-5 days of the kits mail-out, participants will receive a telephone call from the PN. The PN will provide one-on-one education involving three overlapping domains: 1) information on the nature and purpose of cervical cancer screening and the causative role of HR-HPV; 2) the ability to complete screening through a clinic-based Pap test or through self-sample HPV testing using the kit; and 3) instruction on how to use and return the completed kit. Participants who indicate preference to undergo a Pap test will be assisted with scheduling an appointment with a Harris Health provider. Participants who indicated intent to self-sample but whose kit is not received by the lab within 3 weeks of mail-out will receive up to 3 telephone reminders and a letter if unreachable by phone. Arm 3 will also receive information on telehealth options available for Harris Health patients and will be given the phone number for help accessing telehealth.

Mailed self-sample HPV testing (Arms 2 and 3) HPV self-sampling kits will include an introductory letter, research information sheet, self-sampling kit, instructional brochure, and a labeled, pre-paid envelope addressed to the Harris Health central offices. The introductory letter, on behalf of Harris Health, will invite women to use the self-sampling kit as part of a research study to evaluate new strategies for cervical cancer screening. The letter will ask women to complete the self-testing HPV kit as soon as they get the package and return their sample in the mail. The letter will refer patients to the research information sheet, which provides the telephone number for the Harris Health scheduling department, indicates that, as an alternative to a Pap test, participants can complete and return the enclosed self-sampling kit. The research information sheet will describe the study's purpose, procedures, voluntary participation, risks and benefits, and protection of privacy and confidentiality. It will provide a number to call to revoke authorization for review of medical record data and to report injury or other adverse events. The instructional brochure provides illustrated step-by-step instructions in English and Spanish and is written for comprehension at a fourth-grade reading level (see Section Z for attachments in English and Spanish). The self-sampling kit is the commercially-available Aptima Cervical Specimen Collection and Transport Kit (see Section Z for manufacturer's package insert). The kit consists of an individually-wrapped cervical swab and a vial of Aptima Specimen Transport Medium.

Laboratory testing for HR-HPV using self-sampling kits: The vial of specimen transport medium will be returned within a sealed biohazard bag (pre-labeled with the participant ID), which will be placed within a postage-paid padded return envelope, addressed to central Harris Health offices. The Aptima specimen transport vial is approved for shipping via standard mail. The vial will then be routed by PNs to the central CLIA-certified laboratory at Harris Health. HPV testing on self-sampled kits will be conducted using the FDA-approved Aptima® HPV test (Hologic), which is the same assay used for standard of care clinical HPV testing. Aptima tests for 14 high-risk HPV types, including HPV 16 and 18. Per routine standard of care, HPV-positive samples will be reflex-genotyped for HPV 16 and 18/45 (the genotypes associated with 80% of invasive cervical

cancers worldwide) to improve risk stratification and determine the appropriate algorithm for clinical follow-up. As is standard, test results will be interpreted as 1) HR-HPV negative, 2) HR-HPV positive and HPV 16/18/45 negative; 3) HR-HPV positive and HPV 16/18/45 positive; or 4) inadequate (due to unsatisfactory sample). Kits that are returned after >30 days will also be considered inadequate.

Test results will be sent via Harris Health secure transmission to co-investigator [name], the study coordinator, and the PN team. Notification of test results and referral for clinical follow-up: HR-HPV positive test results will be communicated on a weekly basis to co-investigator [name]. [name] will be responsible for referring HR-HPV positive women to clinical follow-up. Notification to participants of both negative and positive results will be conducted by the PNs, who will contact participants by telephone within 10 days of the laboratory's receipt of the sample. Participants who are unreachable after 3 telephone attempts on different days/times will be mailed their results by certified mail. Results will be reported as follows: HR-HPV negative women will be told that no high-risk HPV strains were found in their sample. However, since self-sampling is not currently approved for primary screening, women will be advised to attend for clinic-based screening within the next 12 months. [name] is now affiliated with MD Anderson and will continue to provide clinical oversight for the trial and review lab results through the secure Harris Health EMR system. MD Anderson has been added as a site for this study with the BCM IRB. HR-HPV positive. Women who test positive for HR-HPV but negative for 16/18/45 will be referred by [name] to clinic-based screening (Pap/HR-HPV co-testing). They will be asked to make an appointment with their healthcare provider and given clinic contact information. Women who test positive for HR 16/18 will be referred to colposcopy. As is standard practice at Harris Health when screening abnormalities are encountered, women requiring follow-up Pap test screening or colposcopy who have not made an appointment within 30 days of test result notification will receive a telephone call from a PN who will assist them with scheduling an appointment.

Inadequate: Women whose samples were inadequate (due to unsatisfactory sampling or kit returned after >30 days) will be advised to attend for clinic-based screening or mailed a new kit.

Ascertainment of Outcomes Primary outcome. The primary outcome is primary screening participation, defined as completion and return of a mailed self-sample HPV testing kit that is tested in the lab or attendance for clinic-based screening within 6 months of randomization. Receipt of mailed self-sample HPV testing kits will be ascertained by reviewing lab records. Attendance for clinic-based screening will be ascertained by the study coordinator based on review of the Harris Health EMR. Primary screening participation will be dichotomously categorized as screened/unscreened. Secondary outcomes are screening tests results (positive, negative, or inadequate) and completion of clinical follow-up among women with an abnormal screening test result (attended, did not attend). Screening test results will be ascertained within 6 months of randomization. Pap/HR-HPV co-testing results will be ascertained by EMR review. Self-sample HR-HPV test results will be based on laboratory reports. Completion of clinical follow-up will be ascertained by EMR review within 6 months of the date of the screening test result. Completion of clinical follow-up is defined as attendance for colposcopy among participants who had a positive test by clinic-based screening and attendance for colposcopy or subsequent clinic-based screening among those who had a positive test by self-sampling. Additional exploratory outcomes (sub-aim 2) are detection and treatment of cervical precancers (i.e., histologically-confirmed cervical intraepithelial neoplasia grade II or greater [CIN2+]). Precancers will be ascertained by EMR review within 6 months of abnormal screening results and treatment as per ASCCP guidelines will be ascertained within 6 months of the date of diagnosis. Completion of primary care appointments will be ascertained at 6 months, including telehealth appointments. Additional variables will be collected to meet the aims of the NIH-funded supplement (3R01MD013715-04S1) to the parent trial: HIV status, Preventive Care Gap Score, Enrollment in MyHealth portal, History of COVID-19 diagnosis, HPV vaccination status and Risk of Admission or ED visit. We will also collect Mental and Behavioral Disorders due to use of the following: alcohol (Code F10), opioids (Code F11), cannabis (Code F12), sedatives, hypnotics, anxiolytics (Code F13), cocaine (Code F14), other stimulants, including caffeine (Code F15),

hallucinogens (Code F16) nicotine (Code F17), inhalants (Code F18) and other psychoactive substances and multiple drug use (Code F19).

Data collection instruments are attached in Section S: Attachments, file name: PRESTIS Forms." Instances of Injury and Adverse Events (AE) will be handled as follows. In the Research Information Sheet, participants will be informed of the risks of using the self-collection device and swab. The sheet will include a definition and examples of adverse events, as well as phone numbers to report an AE to the study team and to make an appointment with a Baylor OB/GYN (see RIS in English/Spanish in Section Z) Participants are considered "on-study" through ascertainment of primary and secondary outcomes described above. While we do not anticipate AEs after the "on-study" period, AEs will be monitored for 90 days after participants go "off-study. Community Advisory Board: We will work with various community partners to serve on the project's community advisory board (CAB). Materials and patient navigator scripts are still being translated from English to Vietnamese by a professional translator and will be submitted via an amendment in BRAIN for IRB review and approval prior to implementation. Facilitated by [name], CAB members will review the documents for linguistic and cultural appropriateness and plain language.

After laboratory testing at Harris Health, the PreservCyt vials will be transferred for storage at BCM, specifically in the DLDCCC Population Science Biorepository (directed by co-investigator [name]). The samples will be banked indefinitely for future IRB-approved research (specifically for HPV testing and validation of HPV tests currently under development).

BCM is the banking institution and has an approved policy for storing specimens. Banked specimens will only be used by investigators listed on this protocol.

The remaining sample will be stored in the DLDCCC Population Sciences Biorepository. Samples will be kept indefinitely. The research information sheet informs subjects that they can revoke authorization for banking of their remaining specimen by calling the PI. If authorization is revoked, the sample will be discarded.

Setting

Harris Health System, Harris Health is the primary safety net provider for the Houston metroplex and provides care for more than 320,000 underinsured or uninsured Harris County residents. In 2017, Harris Health logged over 1.9 million outpatient visits. Patients are billed on a sliding scale based on degree of economic hardship. Minorities represent over 92% of the population, with Hispanics being the largest racial/ethnic group (76%), followed by non-Hispanic blacks (16%). Established in the 1960s, Harris Health currently consists of two general hospitals, a specialty care hospital, an HIV/AIDS treatment clinic, 18 community health clinics, 3 pediatric clinics, 11 homeless clinics, and 5 school-based clinics. Through affiliation agreements between Harris Health, BCM, The University of Texas Health Science Center at Houston, and M.D. Anderson Cancer Center, the academic institutions provide physician staffing to Harris Health facilities.

Harris Health has a state of the art infrastructure of personnel and services to adequately support the randomized controlled trial described in this proposal. Personnel and services are available to provide support in regulatory affairs, study coordination, data safety monitoring, quality control, and quality assurance. Information Technology staff are able to generate monthly EMR-based reports to identify eligible women for the randomized controlled trial and provide technical support for querying the EMR. Harris Health has a sophisticated central CLIA-certified laboratory that processes samples for all the ambulatory care clinics. HR-HPV testing will be conducted in this facility.

The Patient Navigation department at Harris Health is led by [name] (nurse case manager and supervisor). Each navigator has a desktop computer with internet access to the Harris Health-maintained server, Epic, and a network printer.

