2 OBJECTIVES

2.1 Primary Objectives

The overall purpose of this protocol is to evaluate the effectiveness of self-sample HPV testing with patient navigation to increase cervical cancer screening among women who otherwise do not regularly attend for clinic-based screening (i.e., Pap test).

The specific aims of this protocol are to: SPECIFIC AIM 1: Compare the effectiveness of mailed self-sample HPV testing alone and in combination with patient navigation to increase primary screening participation (primary outcome) and clinical follow-up (secondary outcome).

Hypothesis 1.1: Primary screening participation and clinical follow-up will be significantly greater among women randomized to receive telephone recall with mailed self-sampling kits versus telephone recall alone. Hypothesis 1.2: There will be significant incremental gains in screening participation and clinical follow-up among women randomized to receive mailed self-sampling kits in combination with patient navigation.

After receiving an administrative supplement, we have revised the trial to include Asian/Asian American women who are currently under-presented in the trial and in the broader literature on self-sampling. In doing so, we will ensure that the trial is powered to rigorously assess and compare screening participation and other outcomes across racial/ethnic and linguistic subpopulations inclusive of Asian/Asian American women. Collectively, the data generated in pursuit of these aims and those of the larger trial will define the impact of mailed self-sample HPV testing among medically underserved Asian/Asian American and other racial/ethnic minority women in safety net health system settings.

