3.4 Data Analysis

Randomized Controlled Trial Primary outcome. Primary screening participation will be examined dichotomously (screened/not screened) using an "intent-to-screen" analytic approach. Bivariable tables and Pearson's χ^2 tests will be used to compare the proportion of primary screening participation across Arms 1, 2, and 3, as well as the absolute difference in participation across Arms 1, 2 and 3. Bivariable tables and Pearson's χ^2 tests will be used to compare the proportion of primary screening participation by study arm, as well as the absolute difference in participation across arms. Log binomial regression will be used to calculate the relative risks of primary screening participation and corresponding 95% confidence intervals (CIs). Secondary outcomes. Descriptive analyses of secondary outcomes will be conducted using bivariable tables and Fisher's exact tests to describe and compare test results and attendance for clinical follow-up across study arms 1, 2 and 3. Log binomial regression will be used to calculate relative risks and 95% CIs of having a positive screening test and of attending for clinical follow-up.

Analytic sub-aim: 1) We will use descriptive statistics (bivariable tables and chi-square/Fisher's exact tests) to compare characteristics of un/under-screened women and those who are up-to-date on screening across Arms 1, 2, and 3. Multivariable logistic regression will be used to assess the independent association between screening status and participant characteristics. 2) Detection and treatment of precancers will be explored through descriptive analyses using bivariable tables and Fisher's exact tests. 3) Among participants in Arms 1, 2 and 3, we will conduct separate analyses to assess characteristics associated with primary screening participation. For Arms 1, 2 and 3, we will use bivariable tables with Pearson's χ^2 tests to describe characteristics of screened and unscreened participants. Characteristics of interest include age, race/ethnicity, months since last Pap test, health plan type, number of healthcare encounters in the past 12 months, and time enrolled as a Harris Health patient. Associations with $p<0.10$ will be used to determine candidate variables for subsequent multivariable

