Participants who are unreachable after 3 telephone attempts on different days/times will be mailed their results by certified mail. Results will be reported as follows: HR-HPV negative women will be told that no high-risk HPV strains were found in their sample. However, since self-sampling is not currently approved for primary screening, women will be advised to attend for clinic-based screening within the next 12 months.

Women who test positive for HR-HPV but negative for 16/18/45 will be referred by [name] to clinic-based screening (Pap/HR-HPV co-testing). They will be asked to make an appointment with their healthcare provider and given clinic contact information. Women who test positive for HR 16/18 will be referred to colposcopy. As is standard practice at Harris Health when screening abnormalities are encountered, women requiring follow-up Pap test screening or colposcopy who have not made an appointment within 30 days of test result notification will receive a telephone call from a PN who will assist them with scheduling an appointment. Inadequate: Women whose samples were inadequate (due to unsatisfactory sampling or kit returned after >30 days) will be advised to attend for clinic-based screening or mailed a new kit. **Ascertainment of Outcomes**
Primary outcome. The primary outcome is primary screening participation, defined as completion and return of a mailed self-sample HPV testing kit that is tested in the lab or attendance for clinic-based screening within 6 months of randomization. Receipt of mailed self-sample HPV testing kits will be ascertained by reviewing lab records. Attendance for clinic-based screening will be ascertained by the study coordinator based on review of the Harris Health EMR. Primary screening participation will be dichotomously categorized as screened/unscreened. Secondary outcomes are screening tests results (positive, negative, or inadequate) and completion of clinical follow-up among women with an abnormal screening test result (attended, did not attend).

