Screening test results will be ascertained within 6 months of randomization. Pap/HR-HPV co-testing results will be ascertained by EMR review. Self-sample HR-HPV test results will be based on laboratory reports. Completion of clinical follow-up will be ascertained by EMR review within 6 months of the date of the screening test result. Completion of clinical follow-up is defined as attendance for colposcopy among participants who had a positive test by clinic-based screening and attendance for colposcopy or subsequent clinic-based screening among those who had a positive test by self-sampling. Additional exploratory outcomes (sub-aim 2) are detection and treatment of cervical precancers (i.e., histologically-confirmed cervical intraepithelial neoplasia grade II or greater [CIN2+]). Precancers will be ascertained by EMR review within 6 months of abnormal screening results and treatment as per ASCCP guidelines will be ascertained within 6 months of the date of diagnosis. Completion of primary care appointments will be ascertained at 6 months, including telehealth appointments.

Study Calendar A – Editable Example				
	Study Timepoints			
	Screening	Telephone survey	Qualitative Interview	Outcomes chart review
Informed Consent	X			
Demographics	X			
Clinical history	X			
Questionnaire		X	X	X
Intervention: Data collection, questionnaires		X	X	X
Adverse Events Reporting	X	X	X	X

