9.4 Provisions to Monitor the Study to Ensure the Safety of Subjects

Automated data quality control checks will be built into the design of the Oncore database, including logic checks and pop up alerts that require the individual entering data to double check any flagged entries. Each month, the Project Coordinator will conduct an audit of 25% of the EMRs reviewed to determine accuracy of the primary and secondary outcome ascertainment. If errors are encountered, the Project Coordinator will notify the PI and all reviewed charts will be assigned for re-review. Data monitoring will include a continuous review of 100% of adverse events by the PI. Progress toward participant enrollment and delivery of arm-specific interventions will be monitored by the Project Coordinator and staff biostatistician on a weekly basis. Study progress and safety will also be reviewed weekly. Updates, including patient recruitment, retention/attrition, and AEs will be provided to the PI following each of these weekly reviews either by phone, email or in person. In addition to weekly updates provided to the PI, the

PI and project coordinator will plan to have biweekly meetings in person. At each meeting, the Project Coordinator will provide the following information: number of participants entering the study, status with respect to meeting recruitment targets, percentage of patients assessed who enter the study, number of drop outs, percentage of patients at each stage of the project, and percentage of assessments completed at each assessment point. Per institutional requirement an Annual Report will be compiled and will include a de-identified list and summary of AEs. In addition, the Annual Report will address (1) whether AE rates are consistent with pre-study assignments (2) whether all participants met entry criteria (3) whether continuation of the study is justified on the basis that additional data are needed to accomplish the stated aims of the study. The IRB and other applicable recipients will review progress of this study on an annual basis.

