Data to be collected includes the following: Demographics of participants, HPV test results, clinical follow up outcome (attendance for clinical follow-up among patients with a positive HPV test), time to clinical follow-up for patients with a positive HPV test, self-reported adverse events, accrual numbers and percentages, withdrawals, protocol adherence and stopping rules. Plan for Assuring Protocol Adherence: To ensure compliance with delivery of arm-specific interventions the project coordinator will audit the project database weekly to ensure that trial intervention are being delivered according to the protocol (e.g. that self- sampling kits are mailed out within 3 business days of the telephone recall and that patient navigation is delivered 3-5 business days after mailing out of the self-testing kit) Laboratory Compliance: The Project Coordinator will audit the EMR weekly to ensure that HR-HPV testing is completed on returned kits and that the results are reported in the EMR. The project coordinator will be responsible for notifying and ensuring that the clinical co-investigator [name] reviews HR-HPV positive results and determines a clinical management plan according to the algorithm established per the protocol. Reporting of Adverse Events: Potential adverse events associated with self-sampling are comparable to those associated with standard of care clinic-based screening (e.g. light bleeding, slight cramping). In the research letter, participants will be given a telephone number to call to report injury and other adverse events. Adverse events that are reported will be documented on a reporting form and will be graded according to the Common Terminology Criteria for Adverse Events. Adverse events will immediately be brought to the attention of the PI and reported to the IRB.

An annual report will be compiled and will include the de-identified list and summary of AEs. In addition the Annual Report will address (1) whether AE rates are consistent with pre-study assumptions; (2) whether all participants met entry criteria; (3) whether continuation of the study is justified on the basis that additional data are needed to accomplish the stated aims of the study. While we do not expect any serious unanticipated adverse events to occur, these incidents will be reported to the IRB for immediate review as soon as they are brought to the attention of study staff.

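### Minor: the clinical follow-up definition, read literally, counts a kit user referred to colposcopy as having attended after a clinic-based screen alone, a small credit available only in Arms 2 and 3

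*Combined protocol and SAP*

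**What the plan says.** Section 3.1 (Ascertainment of Outcomes) gives two rules for completed clinical follow-up: "attendance for colposcopy among participants who had a positive test by clinic-based screening and attendance for colposcopy or subsequent clinic-based screening among those" whose positive test came from a kit. Section 6.1 repeats the kit rule as "attendance for colposcopy or subsequent clinic-based screening among those who had a positive test by self-sampling". Neither place mentions genotype.

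Referral of kit positives does depend on genotype. Section 3.1 states: "Women who test positive for HR 16/18 will be referred to colposcopy". For the other group, Section 6.1 states: "Women who test positive for HR-HPV but negative for 16/18/45 will be referred by" the responsible co-investigator to clinic-based Pap/HPV co-testing. Both sections carry both referral rules.

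The outcome enters a comparison between arms. Hypothesis 1.1 in Section 2.1 reads "Primary screening participation and clinical follow-up will be significantly greater among women randomized" to recall plus kit than among those given recall alone. Section 3.4 plans Fisher's exact tests to "describe and compare test results and attendance for clinical follow-up across study arms 1, 2 and 3", with relative risks and 95% confidence intervals from log binomial regression.

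**The concern.** For one group of women, the event that counts as completed follow-up is wider than the event they were asked to complete. A 16/18-positive kit user is referred to colposcopy, but a later clinic-based screen also satisfies the definition. A woman positive by clinic-based screening has no such alternative and must attend colposcopy.

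Only Arms 2 and 3 receive kits, so the extra credit cannot arise in Arm 1. Relative to scoring by referral, it can only raise follow-up in the kit arms, which is the direction Hypothesis 1.1 predicts. Hypothesis 1.2 compares two kit arms under the same rule, so it is not systematically affected. The primary outcome does not use this definition.

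The event is possible on the documents' own account. The recall script in the kit arms tells women that they are overdue for a Pap test and asks them to call for an appointment. A Pap test booked on that prompt and done after the kit result would qualify as a subsequent clinic-based screen.

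**Working it through.** **1. Referral and scoring side by side (Sections 3.1 and 6.1)**

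| Positive result | Referred to | Scored as complete after | Agreement |
|---|---|---|---|
| Kit, 16/18 positive | Colposcopy | Colposcopy or clinic screen | No: the scoring is wider |
| Kit, HR-HPV positive, 16/18/45 negative | Clinic co-testing | Colposcopy or clinic screen | Yes: the referred step counts |
| Kit, positive for 45 but not 16/18 | Not stated | Colposcopy or clinic screen | Cannot be judged |
| Clinic-based screen positive | – | Colposcopy | – |

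The third row arises because the result categories group 16/18/45 together, while the colposcopy referral names only 16/18.

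**2. Size of the credit**

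The plan states no expected rate, sample size or power for clinical follow-up, so there is no figure to reproduce. From the documents come 756 women per arm (Section 4) and kit return of 10–39% in earlier trials (Section 1.2). Everything else is assumed:

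- a = attendance at the referred step: 60% (also 40% and 80%), equal by route, so that there is no true difference
- k = kit share of the positives in a kit arm: 0.70
- s = share of kit positives referred to colposcopy: 0.275
- e = share of colposcopy non-attenders who have a clinic screen: 0.30
- screening uptake 15% in Arm 1 and 31% in a kit arm, with 20% positive

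Positives: Arm 1, 756 × 0.15 × 0.20 ≈ 23; kit arm, 756 × 0.31 × 0.20 ≈ 47.

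Kit positives: 0.70 × 47 = 32.9. This implies 32.9 / 0.20 = 164.5 kits, or 21.8% of 756, which lies inside 10–39%.

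Referred to colposcopy: 0.275 × 32.9 = 9.0. Not attending: 0.40 × 9.0 = 3.6. Credited through a clinic screen: 0.30 × 3.6 = 1.1 women.

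Excess in the arm's follow-up proportion = k × s × (1 − a) × e:

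| a | Excess | Women of 47 | Relative risk, 1 + excess/a |
|---|---|---|---|
| 40% | 0.0346 | 1.6 | 1.09 |
| 60% | 0.0231 | 1.1 | 1.04 |
| 80% | 0.0115 | 0.5 | 1.01 |

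If e is 0.05 and a is 60%: 0.70 × 0.275 × 0.40 × 0.05 = 0.0039, or 0.4 points and about 0.2 of a woman.

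**3. Against sampling error**

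The 95% half-width for 23 versus 47 at 60% is 1.96 × √(0.24/23 + 0.24/47) = 0.244, about 24 points. By full enumeration, the chance of Fisher p<0.05 with no true difference moves from 0.038 to 0.042 at a = 60%. The part favouring the kit arm moves from 0.021 to 0.031. At a = 40% the overall chance is 0.044.

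**4. Second set of assumptions**

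Take kit return 20%, kit positivity 15%, 25% of kit positives referred to colposcopy, 15% of those having a clinic screen only, and clinic screening 10% with 10% positive. Kit positives are 756 × 0.20 × 0.15 = 22.7 and clinic positives 756 × 0.10 × 0.10 = 7.6. Credited women are 22.7 × 0.25 × 0.15 = 0.85. The excess is 0.85 / 30.2 = 2.8 points, against a half-width of 1.96 × √(0.25/30.2 + 0.25/7.6) ≈ 40 points. Over 729 combinations around these values the median excess was 2.4 points, and it never exceeded 0.35 of the half-width.

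**The case against.** The strongest reply is that the wording is shorthand for the two referral branches: colposcopy for those sent to colposcopy, clinic screening for those sent to clinic screening. Section 3.1 pairs the two steps in the same way when it describes women who still need an appointment. Section 9.4 says that the clinical co-investigator "determines a clinical management plan according to the algorithm established per the protocol", and the coordinator who oversees that step also runs the monthly "audit of 25% of the EMRs reviewed to determine accuracy of the primary and secondary outcome ascertainment". The data collection forms are attached separately and may hold a finer scoring rule. This stands as a plausible account of intent, and nobody can say from these documents that the trial lacks such a rule. But the definition itself does not tie completion to referral, and an audit against its wording would have no ground to reject the literal scoring.

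A second reply is that the mis-scored event is unlikely. A navigator calls women who have made no follow-up appointment within 30 days and helps them schedule, which steers those referred to colposcopy towards it. This also stands, and it makes the 0.4-point case realistic.

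Third, Section 3.4 already introduces the secondary analyses as descriptive. That is true, although Hypothesis 1.1 speaks of a significant difference and relative risks with intervals are planned.

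A reader might go further and infer that the rule materially distorts the test of Hypothesis 1.1. The documents do not support that. With every assumed input at its top value (k = 0.9, s = 0.40, e = 0.40), the excess is 5.8 points at 60% attendance and the Fisher rejection chance is 0.061. But 90% of 47 positives from kits leaves 4.7 clinic positives. At 20% positivity that is 4.7 / 0.20 = 23.5 women, or 3.1% clinic screening, against 15% in Arm 1. That corner is implausible and should not be relied on.

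**Conclusion.** The definition is wrong as written, and the point is minor. The mismatch between referral and scoring is plain in the text, and its direction is fixed: it can help only the kit arms against Arm 1. Its size rests entirely on assumed rates. At mid-range inputs it is 1.2 to 3.5 points, about one woman per kit arm and well inside sampling error; it is about 0.4 points if few colposcopy non-attenders have a clinic screen. The size grows with the share of colposcopy-referred women who have a clinic screen only, for which the documents give no figure.

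Two further inferences should be resisted. The documents do not show that women will in fact be mis-scored, only that the written rule permits it. Nor would correcting the rule make the Arm 1 comparison a clean randomised contrast. Follow-up would still mean a different event for co-test-referred kit users than for clinic-screen positives, a difference that probably involves more women. The denominator, women with an abnormal screen, is also formed after randomisation.

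**What to change.** 1. Reconcile the referral text with the outcome definition in Sections 3.1 and 6.1, including the 16/18 versus 16/18/45 wording, so that the referred step is stated for every result group. Which referral is intended is for the investigators to say.
2. Define completion as attendance, within the existing 6-month window, at the step to which each woman was actually referred. Use that rule in the EMR review and in the 25% audit.
3. Report completion by screening route. Add one sensitivity analysis of colposcopy attendance among all women with a recorded colposcopy referral.
4. State that the comparison of follow-up with Arm 1 is descriptive, because the route difference and the post-randomisation denominator remain.

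The cost is a sentence or two in the definition and a few tables. Genotype is already in the laboratory result, and screening and follow-up attendance already come from EMR review. The downsides are slightly lower follow-up rates in Arms 2 and 3 and small cells: about nine colposcopy-referred kit users per arm at the mid-range inputs.
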